9.4 Analyses Plans

9.4.1 Analysis Population

Analyses will be performed for all patients. The study will use the NCI CTCAE v4.0.

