2.4 Endpoints

2.4.1 Primary Endpoint

1. The primary endpoint of the study is to determine the rate of acute toxicity (≤ 90 days within the completion of radiotherapy) and late toxicity (≥ 91 days within the completion of radiotherapy). Adverse events will be defined according to CTCAE v. 4.0 criteria. Patients will be monitored at least weekly during treatment and every 3-6 months up to 24 months and at 36 months after radiation therapy.
2. A PSA measurement will be obtained at 120-127 days after initiation of androgen deprivation therapy. The proportion of patients achieving a PSA-CR (PSA nadir ≤ 0.3) at 120-127 days will be determined. The historical proportion of patients (0.7) attaining a PSA-CR from RTOG 9413 will be utilized for comparison.

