6.1 Schedule of Procedures and Observations

Screening assessments must be performed within 8 weeks prior to the first dose of neoadjuvant androgen deprivation therapy. Any results falling outside of the reference ranges may be repeated at the discretion of the investigator. All on-study visit procedures are allowed **a window of ± 14 days** unless otherwise noted. Treatment or visit delays for public holidays or weather conditions do not constitute a protocol violation.

A written, signed, informed consent form (ICF) and a Health Insurance Portability and Accountability Act (HIPAA) authorization must be obtained before any study-specific assessments are initiated. A copy of the signed ICF will be given to the subject and a copy will be filed in the medical record. The original will be kept on file with the study records.

All patients who are consented will be registered in OnCore[®], the UCSF Helen Diller Family Comprehensive Cancer Center Clinical Trial Management System (CTMS). The system is password protected and meets HIPAA requirements.

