9.2 Determination of Sample Size and Accrual Rate

9.2.1 Sample Size and Power Estimate

Sample size is determined based on the primary objective of the PSA-CR. This is a single arm study with the primary endpoint evaluating the proportion of patients experiencing a PSA-CR. From historical controls (RTOG 9413 and MSKCC as mentioned in background information), we expect 70% of patients to experience a PSA-CR. With addition of enzalutamide, at least 85% of patients are expected to attain a PSA-CR. With 53 patients (10% dropout rate), we would have 80% power to detect thus improvement at significance level of 0.05 based on directional binomial test.

As we expect the combined enzalutamide and leuprolide regimen does not significantly increase grade 3 or greater acute or late toxicity for treatment of intermediate- to high-risk prostate cancer and the usual rate of 3 or greater toxicity is approximately 12%. If the true grade 3 or greater acute or late toxicity rate is 12%, with 47 patients we will have 80% confidence in the toxicity rate estimate with precision of 4.7% (i.e. a confidence interval width of 9.4%).

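### The 80% power for PSA-CR assumes the 10% dropouts leave the denominator, while the only stated analysis set is all patients and no rule covers a missing day 120-127 PSA

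*Combined protocol and SAP*

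**What the plan says.** All references are to the combined protocol and SAP.

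- **Analysis set.** Section 9.4.1 gives a single rule: "Analyses will be performed for all patients". Section 9.4.2 then compares PSA-CR with the historical rate by binomial test and mentions no evaluable subset.
- **Sample size.** Section 9.2.1 takes the historical rate as the null ("we expect 70% of patients to experience a PSA-CR") and sets the alternative with "With addition of enzalutamide, at least 85% of patients are expected to attain a PSA-CR". The test is at a "significance level of 0.05 based on directional binomial test". The claim is "With 53 patients (10% dropout rate), we would have 80% power". The same section uses 47 patients for its toxicity precision statement.
- **Endpoint.** Section 2.4.1 fixes one measurement: "A PSA measurement will be obtained at 120-127 days after initiation of androgen deprivation therapy". It names the comparator as 0.7.
- **Visit windows.** Section 6.1 gives a general allowance of 14 days either side unless otherwise noted ("All on-study visit procedures are allowed" is how the sentence begins). Section 2.4.1 has its own, narrower window.
- **After stopping treatment.** Section 3.3 (Discontinuation Criteria) continues follow-up and data collection when a patient stops protocol treatment or progresses.

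No section says how a patient without a PSA in the day 120-127 window is counted.

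**The concern.** A dropout allowance that leaves the response rate at 85% works only if dropouts are removed from both numerator and denominator. An analysis of all patients keeps them in the denominator. To stay in a binomial proportion, a patient with no PSA must be given a value, and the usual choice for a response endpoint is non-response. That lowers the rate the trial can be expected to observe, and the sample size does not allow for it.

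PSA-CR is the endpoint that sized the trial. If the denominator is left open, it can be settled after the data are seen, and near the rejection boundary a few patients decide the result. With 53 analysed, the test rejects at 43 responders but not at 42.

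**Working it through.** **Inputs.** Null 0.70, alternative 0.85, one-sided 5% level, 53 enrolled and 10% dropout, all from section 9.2.1. The null is repeated in section 2.4.1. The denominator of all patients is from section 9.4.1.

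**Step 1: reproduce the plan's figure.** Arcsine approximation, one-sided:

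- Effect: 2·asin(√0.85) − 2·asin(√0.70) = 2.3462 − 1.9823 = 0.3639.
- n = ((1.6449 + 0.8416) / 0.3639)² = 46.7, so 47.
- 47 / 0.9 = 52.2, so 53.
- Power at 47 = Φ(0.3639 × √47 − 1.645) = Φ(0.850) = 80.2%.

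Both 53 and 80% reproduce, and 47 is the number section 9.2.1 uses for toxicity. The 80% therefore refers to about 47 evaluable patients, with dropouts outside the denominator.

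**Step 2: the same evaluable-only design under an exact test.** For each n, take the smallest cutoff c with P(X ≥ c | n, 0.70) ≤ 0.05, then compute P(X ≥ c | n, 0.85).

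| n | Reject at | Actual one-sided level | Exact power at 85% |
|---|---|---|---|
| 47 | 39 | 0.033 | 73.3% |
| 48 | 40 | 0.027 | 71.2% |
| 53 (nobody missing) | 43 | 0.048 | 83.8% |

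At 10% dropout (47 or 48 evaluable), exact power is below 80% even when dropouts are removed as section 9.2.1 assumes.

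**Step 3: all 53 in the denominator.** Assumptions: a missing PSA counts as not PSA-CR, patients with a PSA respond at 85%, and the null stays at 0.70. If a share m is missing, the expected rate is 0.85 × (1 − m), and power is P(X ≥ 43 | 53, 0.85(1 − m)).

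| Missing PSA | Expected rate | Exact power |
|---|---|---|
| 0% | 0.850 | 83.8% |
| 2% | 0.833 | 73.7% |
| 5% | 0.8075 | 55.5% |
| 8% | 0.782 | 37.4% |
| 10% | 0.765 | 26.9% |

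**Step 4: compare like with like at 10%.** By the exact test, evaluable-only at 47 against all 53 is 73.3% against 26.9%. By the arcsine approximation it is 80.2% against 28.3%.

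**Step 5: how far the 10% row depends on the fixed null.** If the historical rate were also deflated by 10%, to 0.70 × 0.9 = 0.63 (an assumption), the cutoff at n = 53 would be 40 and power at 0.765 would be 64.2%.

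**The case against.** A reader might infer that power falls from 80% to about 27%. The documents do not support that as a headline, for four reasons:

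- It sets an arcsine 80% beside an exact 27%.
- It needs every one of the 10% dropouts to lack a day 120-127 PSA. Section 9.2.1 does not say when dropout occurs, treatment runs for 24 months, and section 3.3 continues data collection after treatment stops. A patient who stops treatment or leaves after day 127 can still have the measurement.
- The scoring rule behind it is not in the plan.
- It holds the null at 70%, and the documents do not show how the historical studies counted missing PSAs. Step 5 shows that this matters.

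A reader might also call the two sections a deliberate contradiction. Section 9.4.1 goes straight on to CTCAE, and section 7.2 on safety has almost the same sentence, so the text may have been carried over from safety. All patients may also mean all treated patients, since section 5.1 allows up to 14 weeks between enrollment and the start of treatment. This weakens the charge of contradiction. It does not supply a PSA-CR denominator, and section 9.4.1 remains the only analysis set named.

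A third inference is that analysing completers only would inflate the false-positive rate. That depends on an assumed response rate r among dropouts. With an all-patient rate of 70%, completers show (0.70 − 0.1r)/0.9. At r = 30% this is 74.4%, and the chance of rejection at n = 47 is 11.7%. At r = 50% and n = 48 it is 5.5%. At r = 60% it is 3.9-4.6%, below 5%. The documents give no value for r, so inflation is possible but not shown.

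What stands is that the stated power and the stated analysis set do not match, and the missing-PSA rule is absent.

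**Conclusion.** The point holds as a mismatch between sections 9.2.1 and 9.4.1-9.4.2. The 80% power belongs to about 47 evaluable patients and an approximation. At the plan's own 10% dropout, the exact test gives 73.3% or 71.2% if dropouts are removed (47 or 48 evaluable). If they stay in and all lack the PSA, it gives 26.9%. Neither reading delivers 80%.

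On the all-patient reading, the defensible statement is a range: 83.8% with no PSA missing, 73.7% at 2%, 55.5% at 5%, and 26.9% at 10% as the worst case. The range assumes that a missing PSA scores as not PSA-CR, that patients with a PSA respond at 85%, and that the null stays at 70%. The documents give no figure for how many patients will miss the window, so the point within the range is unknown.

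**What to change.** **Section 9.4.1**, add for PSA-CR:

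- Primary set: all patients who received at least one dose of protocol androgen deprivation.
- Value: the PSA measured on day 120-127, used whether or not the patient is still on treatment. This is consistent with section 3.3 and keeps the section 2.4.1 endpoint unchanged.
- Patients with no PSA in that window count as not PSA-CR.
- Sensitivity analyses: (a) only patients with a PSA in the window; (b) a PSA accepted within a symmetric 14-day allowance, that is day 106 to 141 (120 − 14 to 127 + 14). The allowance should run both ways, because a late-only extension gives more time on treatment and could favour response.

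**Section 9.2.1**: restate power by the exact one-sided binomial test for this set over 0-10% missing. State the cutoff (43 of 53 if all 53 are treated) and that the null is held at 70%.

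**Cost**: protocol/SAP wording and a less favourable stated power. The change needs no extra patients or visits. It does not restore 80% power; it makes the power claim match the analysis and fixes the denominator before the data are seen.

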9.4.2 Primary Analysis (or Analysis of Primary Endpoints)

Point estimates and 95% confidence intervals of PSA-CR will be obtained. The PSA-CR will be compared with the historical rate by binomial test.

Toxicity will be assessed by CTCAE v4.0. Point estimation and its 95% confidence interval will be calculated for the rate of acute Grade 3 or greater toxicity within 24 months of completing treatment with radiotherapy. Furthermore, one sample proportion test will be used to test hypothesis that the addition of enzalutamide to leuprolide and radiation therapy does not significantly increase acute or late toxicity.

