3.5 Duration of Therapy

In the absence of treatment delays due to adverse events, treatment may continue for up to 24 months or until:

- Disease progression
- Inter-current illness that prevents further administration of treatment
- Unacceptable adverse event(s)
- Patient decides to withdraw from the study
- Significant patient non-compliance with the protocol
- General or specific changes in the patient's condition render the patient unacceptable for further treatment in the judgment of the investigator.

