7.1 Definitions

Evaluable for toxicity

All patients will be evaluable for toxicity from the time of their first treatment with the study drug until 24 months after last dose of enzalutamide treatment.

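### The grade 3+ toxicity rate to 24 months after radiotherapy is a simple proportion over all patients with no allowance for incomplete follow-up, which biases it downward

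*Combined protocol and SAP*

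**What the plan says.** Section 2.4.1 makes toxicity the first primary endpoint and splits it into acute (up to 90 days after radiotherapy) and late (from day 91).

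Section 9.4.2 gives the analysis: "Point estimation and its 95% confidence interval will be calculated for the rate of acute Grade 3 or greater toxicity within 24 months". The window is counted from the end of radiotherapy. The same section then plans a hypothesis test: "one sample proportion test will be used to test hypothesis that the addition of enzalutamide to leuprolide and radiation therapy does not significantly increase". That test is meant to cover the acute and the late period alike.

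On who is counted, section 9.4.1 says "Analyses will be performed for all patients". Section 7.1 says "All patients will be evaluable for toxicity from the time of their first treatment with the study drug until 24 months". The end of that period is counted from the last enzalutamide dose, and no minimum follow-up is set. Section 9.2.1, however, bases the toxicity precision on fewer patients: "with 47 patients we will have 80% confidence in the toxicity rate estimate".

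On loss, section 9.2.1 gives one figure, in the PSA-CR sizing: "With 53 patients (10% dropout rate), we would have 80% power". Section 3.3 continues data collection after a patient stops protocol treatment or progresses. Section 3.5 separately lists "Patient decides to withdraw from the study" as a reason for ending treatment, and section 3.3 does not cover such a patient.

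Kaplan-Meier estimation appears only in section 9.4.3, for secondary endpoints.

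**The concern.** A one-sample proportion test needs a count of events over a fixed number of patients. Over a window that runs to 24 months after radiotherapy, a patient who leaves at month 2 fills a full place in that denominator but can contribute events from two months only. The unobserved time is in effect treated as free of toxicity.

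The direction is what matters. For PSA-CR, counting a missing patient as a non-responder is conservative. For toxicity, counting a missing patient as event-free favours the conclusion the plan hopes to reach, that toxicity is not raised above the 12% reference. Late toxicity is the most exposed part, because a patient lost before day 91 cannot have a late event recorded.

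**Working it through.** **Inputs**
- Reference toxicity rate p = 12%; enrolled 53; toxicity precision on 47 (section 9.2.1).
- Dropout d = 10%, from the PSA-CR sizing (section 9.2.1). Applying it to 24 months is an assumption. The share implied by the plan's own two numbers is 6/53 = 11.3%.

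**The plan's own figures**
- 47 and 53 are linked by dropout: 53 × 0.9 = 47.7, rounded down to 47; and 47/0.9 = 52.2, rounded up to 53.
- The plan states a precision of ±4.7 points at 80% confidence. This does not reproduce. The standard error is √(0.12 × 0.88/47) = 4.74 points, so the stated figure is one standard error (about 68% confidence). The 80% half-width is 1.2816 × 4.74 = 6.1 points, and the 95% half-width is 1.96 × 4.74 = 9.3 points. That is a separate error, and the present point does not rest on it.

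**Size of the bias**

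Let f be the share of a dropout's 24-month risk already observed before leaving. If dropout is unrelated to toxicity and all patients are in the denominator,

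reported rate = p × [1 − d × (1 − f)].

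For even loss over 24 months with constant hazard, λ = −ln(0.88)/24 = 0.00533 per month. The average risk observed in a dropout is 1 − 0.12/(24λ) = 1 − 0.12/0.1278 = 0.0613, so f = 0.0613/0.12 = 0.51.

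| Case (true rate 12%) | d | f | Reported | Shortfall, points | Shortfall, relative |
|---|---|---|---|---|---|
| All dropouts leave with nothing observed | 6/53 | 0 | 10.6% | 1.4 | 11.3% |
| Same | 10% | 0 | 10.8% | 1.2 | 10.0% |
| Even loss | 6/53 | 0.51 | 11.3% | 0.7 | 5.5% |
| Even loss | 10% | 0.51 | 11.4% | 0.6 | 4.9% |
| Events mostly early | 10% | 0.75 | 11.7% | 0.3 | 2.5% |
| Events nearly all early | 10% | 0.90 | 11.9% | 0.1 | 1.0% |

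For late toxicity taken alone, anyone lost before day 91 has f = 0, so the relative shortfall in the late rate equals the share lost by then.

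**If dropout is related to toxicity**

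The formula then gives no upper limit. Suppose 12% of 47 completers have an event (5.64 expected) and all six dropouts have an event that is never recorded. The reported rate is 5.64/53 = 10.6%; the true rate is (5.64 + 6)/53 = 22.0%. This is an extreme, shown only to mark the range.

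**Denominator**

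The same six events give 6/53 = 11.3% or 6/47 = 12.8%. The two results fall on opposite sides of 12%, and the plan does not settle which is meant.

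**The case against.** Several points on the other side are sound.

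- **The rule is implied, not written.** A reader might infer that the plan declares dropouts free of toxicity. It does not. The result follows from a proportion taken over all patients with no other rule. The 47 in section 9.2.1 could mean that an evaluable set was intended; with 47 over 47 the bias calculated above disappears. That stands, but then the evaluable set must be defined, because sections 9.4.1 and 7.1 say otherwise.
- **The 10% belongs to another endpoint.** A reader might take an 11% understatement as the expected size. The dropout figure sits in the PSA-CR sizing, and for that endpoint "A PSA measurement will be obtained at 120-127 days after initiation of androgen deprivation therapy". No 24-month loss is stated. Stopping treatment is not loss to follow-up under section 3.3, and section 3.6 follows patients removed for toxicity until their events settle. The 11.3% is relative, needs all six dropouts to leave with nothing observed, and amounts to 1.4 points.
- **It is small beside sampling error.** The 95% half-width is about 9 points. True, but the bias has one direction, and a wider sample interval does not correct it.
- **Loss of power.** One might infer a large loss. Assuming an exact one-sided 0.05 test against 12% (section 9.4.2 gives neither level nor direction), the cut-off is 11 events with 53 in the denominator and 10 with 47. If only 47 were observed, power at a true 20% is then 33% against 47%. This comes from the discreteness of the cut-off: with 48 observed it is 11 under either denominator, and power is 36.1% both ways. No power claim should be made.
- **Ascertainment is good early on.** Adverse events are assessed weekly during radiotherapy and serious events are reported promptly. If most grade 3+ events are early, the bias is a few tenths of a point. If the endpoint really means acute toxicity to 90 days, it shrinks further; but section 9.4.2 says 24 months, and its test covers late toxicity.

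**Conclusion.** The point holds as one of method and direction. Followed as written, sections 9.4.1, 9.4.2 and 7.1 give a crude proportion over a 24-month window with no allowance for patients not observed throughout. That biases a primary safety rate downward, toward no increase over 12%.

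The likely size is modest: about 0.6 points at a true 12% if 10% are lost evenly, and 1.2 to 1.4 points if all leave with nothing observed. These figures assume that the PSA-CR dropout carries over to 24 months, that loss is unrelated to toxicity, and that the denominator is 53. Early events make the bias smaller; toxicity-related withdrawal makes it larger, so 1.4 points is not a ceiling.

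Two inconsistencies add to the problem: 53 against 47 as the toxicity denominator, and acute toxicity counted to 24 months in section 9.4.2 against 90 days in section 2.4.1.

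**What to change.** In section 9.4.2:

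1. Estimate the cumulative incidence of first grade 3 or greater toxicity to 24 months after radiotherapy. Censor at the last adverse event assessment and treat death without toxicity as a competing event. Compare the estimate and its 95% CI with 12%.
2. Report acute toxicity (to 90 days) and late toxicity (from day 91, among patients still under observation) separately, and reconcile the wording of the 24-month endpoint with section 2.4.1.
3. Keep the crude proportion as a supporting figure, with its denominator stated and reconciled with the 47 in section 9.2.1.

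Censoring assumes that withdrawal is unrelated to toxicity, so reasons for withdrawal should be tabulated beside the estimate.

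The cost is a change of SAP wording, slightly more analysis and a slightly wider interval. It needs the onset date of each event and the date of the last assessment, and no extra patients or visits.

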3.4 Criteria for Termination of Protocol

The trial will be terminated if there is a greater than 12% clinically significant, treatment-Phase II – Enzalutamide and Radiation

related grade 3 or higher toxicity. The 12% clinically significant, treatment-related acute grade 3 or higher toxicity rate is acceptable as prior studies have demonstrated a 12% acute grade 3 GU and GI toxicity. The use of a urinary catheter or bladder irrigation within 14 days after brachytherapy will not be considered grade 2 toxicity as this may be a standard procedure after brachytherapy. The trial will not be terminated for non-related or non-clinically significant toxicities.

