9.3 Interim Analyses and Stopping Rules

Continuous safety monitoring will be performed throughout the trial. The trial will be terminated if there is a greater 12% acute grade 3 toxicity. This rate is acceptable as prior studies have demonstrated 8-15% acute grade 3 GU and GI toxicity when irradiating the pelvis using standard fractionated technique to 45 Gy in 1.8 Gy fractions followed by brachytherapy boost

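### Section 2.4.1 names two primary toxicity rates, acute and late, but 9.4.2 estimates only one; the toxicity precision stated in 9.2.1 is one standard error, not an 80% half-width

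*Combined protocol and SAP*

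**What the plan says.** Section 2.4.1 lists as primary the "rate of acute toxicity (≤ 90 days within the completion of radiotherapy) and late toxicity (≥ 91 days within the completion of radiotherapy". Patients are monitored at least weekly during treatment, then "every 3-6 months up to 24 months and at 36 months after radiation therapy". No end is set for the late period.

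Section 9.4.2 plans a point estimate and 95% confidence interval for "the rate of acute Grade 3 or greater toxicity within 24 months of completing treatment with radiotherapy". It adds a one-sample proportion test of the hypothesis that adding enzalutamide "does not significantly increase acute or late toxicity".

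Section 9.2.1 supplies the benchmark: "the usual rate of 3 or greater toxicity is approximately 12" per cent. Taking 12% as the true rate of acute or late toxicity, it states that with 47 patients "we will have 80% confidence in the toxicity rate estimate with precision of 4.7" points, an interval width of 9.4 points.

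The support cited for 12% is narrower. Section 3.4 says that "prior studies have demonstrated a 12% acute grade 3 GU and GI toxicity", and section 9.3 that "prior studies have demonstrated 8-15% acute grade 3 GU and GI toxicity".

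Sections 7.2 and 9.4.1 say that all patients are analysed.

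**The concern.** Toxicity is a primary endpoint, and the split at day 90/91 is the trial's own definition. The analysis section does not carry it through. Most of a 24-month window after radiotherapy is late by 2.4.1, so a figure reported under the 9.4.2 label would not be the acute rate that 2.4.1 defines. The late rate appears only inside a pooled test. Elsewhere, 7.2 plans a summary of maximum severity without an acute/late split, and 9.4.3 has no toxicity analysis.

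The late period matters for this question, because most of the 24 months of enzalutamide falls within it. The plan also promises a more precise toxicity estimate than its own inputs give. And it words its hypothesis so that a non-significant result could be taken as reassurance, which the sample size does not support.

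**Working it through.** **Windows side by side**

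| Section | Toxicity window |
|---|---|
| 2.4.1 | Acute to day 90 after radiotherapy; late from day 91, no end; visits to 24 months and at 36 months |
| 9.4.2, estimate | One rate, labelled acute, to 24 months after radiotherapy |
| 9.4.2, test | Acute or late, no window |
| 7.1 | Evaluable until 24 months after the last enzalutamide dose |
| 7.3.2 | Adverse events followed to 60 months from the start of androgen deprivation |

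By 2.4.1, about 3 of the 24 months in the 9.4.2 window are acute and about 21 are late.

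Share of drug exposure in the late window, assuming enzalutamide starts on day 0 and a brachytherapy boost follows directly: the synopsis schema starts radiotherapy on day 53-67, and 5 weeks (35 days) brings its end to day 88-102. Adding 90 days closes the acute window on day 178-192, about month 6. Some 18 of the 24 drug months then fall in the late window.

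**Precision in 9.2.1**

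Inputs from 9.2.1: p = 0.12, n = 47, stated half-width 0.047 at 80% confidence.

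- Standard error: √(0.12 × 0.88 / 47) = 0.0474. The stated 4.7 points matches this with no normal multiplier.
- Confidence attached to ±0.047: 2Φ(0.047 / 0.0474) − 1 = 0.679.
- 80% half-width: 1.2816 × 0.0474 = 0.0607, or 6.1 points (width 12.1).
- 95% half-width: 1.96 × 0.0474 = 0.0929, or 9.3 points (width 18.6).
- Patients needed for ±4.7 points at 80%: 0.1056 × (1.2816 / 0.047)² = 78.5, so 79.
- With all 53 patients: standard error √(0.1056 / 53) = 0.0446; half-widths 5.7 points (80%) and 8.7 points (95%).

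Other intervals do not recover 4.7 at 80% confidence. With 6/47 events, the Wilson half-width is 6.3 points and the Clopper-Pearson 7.2. A one-sided 80% bound lies 4.0 points from the estimate.

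**What a non-significant test would mean**

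Assumptions: null 12%, exact binomial, one-sided 0.05. The 12% is read from 9.2.1; the level is assumed, because the 0.05 in 9.2.1 is given for PSA-CR.

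| n | Declare an increase at | P(reject) at 12% | P(miss) at true 20% | True rate with 80% power |
|---|---|---|---|---|
| 47 | 10 or more | 0.0495 | 0.529 | about 25.6% |
| 53 | 11 or more | 0.0476 | 0.500 | about 24.9% |

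At one-sided 0.025 and n = 47 the cut-off is 11 and a true 20% is missed with probability 1 − 0.333 = 0.667.

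**Whether one 12% benchmark can serve**

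The cited support is acute GU and GI toxicity. If acute and late rates were each 12% (an assumption for illustration), the proportion with either would lie between 12% and 24%, and would be 1 − 0.88² = 22.6% under independence. A benchmark for one window therefore does not carry over to a pooled or late rate without justification.

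**The case against.** The strongest reply is that *acute* in 9.4.2 is a dropped phrase. Section 9.2.1 speaks of acute or late toxicity, and so does the next sentence of 9.4.2. That is a plausible reading and it removes the mislabelling. It still leaves one pooled rate where 2.4.1 names two.

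A reader might infer that the toxicity test cannot be carried out. The documents do not support that. Section 9.2.1 uses nearly the same wording as the hypothesis, so the 12% null and the upward direction can be read from it. The unstated significance level and formal sidedness are missing detail, not an error in themselves.

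A reader might also say that 9.2.1 makes the estimate look twice as precise as it is. That sets an 80% claim against a 95% interval. Like for like, the error is 4.7 against 6.1 points; the remaining gap to 9.3 is a change of confidence level, not faulty arithmetic.

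Nor does it follow that excess toxicity would pass unnoticed until the final test. Sections 3.4 and 9.3 call for termination above 12%, which at n = 47 is 6 events (12.8%). Section 9.3 concerns acute grade 3 toxicity and 3.4 treatment-related, clinically significant events, so the weak test matters mainly for events outside those terms, late ones above all.

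Finally, the sample size was set on PSA-CR. Low power for toxicity is a limitation to acknowledge and does not contradict any stated claim.

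**Conclusion.** The point holds in two parts. First, 9.4.2 does not estimate the two primary rates of 2.4.1, and under either reading of its wording the late rate has no estimate or interval of its own. This rests on the text alone. Second, the precision in 9.2.1 is wrong at its own confidence level: 6.1 points, not 4.7, at 12% and 47 patients, and 9.3 points at the 95% level of the planned analysis. With 53 patients the figures are 5.7 and 8.7. These are normal-approximation half-widths.

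The caution about the test is conditional. With a 12% null and one-sided 0.05, a true 20% rate is missed 53% of the time at n = 47 and 50% at n = 53.

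It would go too far to say that month 36 must end the late window. Section 2.4.1 sets no end, month 36 is a visit, and 7.1, 7.3.2 and 9.4.2 each give a different limit. The defect is that these are not reconciled.

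**What to change.** 1. In 9.4.2, estimate two rates of grade 3 or higher toxicity, acute (to day 90 after radiotherapy) and late (from day 91), each with a 95% confidence interval. State one end of the late window, reconciled across 2.4.1, 7.1, 7.3.2 and 9.4.2, and say how incomplete follow-up is allowed for. A time-to-event estimate is one option.
2. In 9.2.1, restate the precision at 12% and n = 47 as about 6.1 points (80%) or 9.3 points (95%). If all 53 patients are analysed, give 5.7 and 8.7.
3. Base the toxicity conclusion on the planned interval, and say that a non-significant one-sample test does not show absence of an increase. Use 12% as a formal null for the acute rate only, stating the event set, since its cited support is GU and GI events. Keep the late comparison descriptive unless a late benchmark is justified.

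The cost is mainly wording and a little more analysis. Grade 3 and higher events are already recorded (7.4) and adverse-event visits already run to month 36 (6.1.4). One dependency remains: under 7.1, a patient who stops enzalutamide early may cease to be evaluable before month 36, so a later cut-off needs that section aligned. The stated precision becomes wider, and the late comparison may end up without a formal test.

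### The 9.4.2 toxicity test has no margin or unacceptable rate, so as worded a non-significant result in 53 patients would be read as showing no added toxicity

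*Combined protocol and SAP*

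**What the plan says.** Safety and feasibility form the first primary objective (2.1), and the acute and late toxicity rates are the first primary endpoint (2.4.1).

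Section 9.4.2 plans a point estimate with a 95% confidence interval for acute grade 3 or greater toxicity, counted over 24 months after radiotherapy. It then adds, for toxicity both acute and late, that a "one sample proportion test will be used to test hypothesis that the addition of enzalutamide to leuprolide and radiation therapy does not significantly increase". It names no reference rate, margin, alpha, sidedness or decision rule for this test.

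The reference rate has to be taken from 9.2.1, which says "As we expect the combined enzalutamide and leuprolide regimen does not significantly increase grade 3 or greater acute or late toxicity" and that "the usual rate of 3 or greater toxicity is approximately 12" percent. The same section sets the sample size on PSA-CR, "at significance level of 0.05 based on directional binomial test". Toxicity gets only a precision statement there.

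Section 9.3 uses the same figure as a stopping boundary: "The trial will be terminated if there is a greater 12% acute grade 3 toxicity". Section 3.4 gives a 12% rule as well, but for clinically significant, treatment-related events of grade 3 or higher.

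**The concern.** The claim the trial hopes to make is that there is no significant increase. In a test of a 12% null against a higher rate, that claim corresponds to failing to reject. Failing to reject shows only that the data did not rule out 12%. It does not rule out a materially higher rate, and a small sample makes that outcome more likely. With no stated rate to be excluded, nothing in 9.4.2 ties the result to a bound on toxicity.

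A second difficulty comes from 9.3. The boundary that ends the trial equals the test's presumed null rate. If both count the same acute events, a trial that reaches its analysis has already been selected to have an observed rate of 12% or less. Testing that rate against 12% is then uninformative, and the estimate itself is pulled down.

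At stake is the primary safety conclusion: the report could state no significant increase while its own data remain compatible with a rate well above 12%.

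**Working it through.** **Inputs.** Reference rate 12% (9.2.1). N = 53 (9.2.1), all patients analysed (9.4.1). With the assumed 10% dropout, 47 or 48 are evaluable. One-sided 0.05 is stated in 9.2.1 for PSA-CR only; using it for toxicity is an assumption, so one-sided 0.025 is shown too. The true rates of 18% and 20% are scenarios chosen here; 9.3 cites 8-15% for prior acute grade 3 toxicity.

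**The plan's own toxicity figure.** Section 9.2.1 gives 80% confidence and 4.7% precision with 47 patients at a true 12%. The standard error is √(0.12 × 0.88 / 47) = 4.7%. The 80% half-width is 1.2816 × 4.74% = 6.1%. The stated figure is therefore one standard error (about 68% confidence) and does not reproduce. This is a separate matter, but it shows that the only design figure for toxicity does not support the test either.

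**Cut-off.** The exact test rejects at the smallest r with P(X ≥ r | n, 0.12) ≤ alpha. For n = 53 and alpha 0.05, P(X ≥ 10) = 0.097 and P(X ≥ 11) = 0.048. So r = 11, which is 11/53 = 20.8%.

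**Chance of a non-significant result**, P(X ≤ r − 1 | n, p), ignoring the stopping rule:

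| n | one-sided alpha | r | true 18% | true 20% |
|---|---|---|---|---|
| 53 | 0.05 | 11 | 0.65 | 0.50 |
| 53 | 0.025 | 12 | 0.76 | 0.63 |
| 48 | 0.05 or 0.025 | 11 | 0.76 | 0.64 |
| 47 | 0.05 | 10 | 0.67 | 0.53 |
| 47 | 0.025 | 11 | 0.79 | 0.67 |

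At a true 20% the range is 0.50 to 0.67.

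**What a non-significant result leaves open.** The exact one-sided 95% upper limit is the p that solves P(X ≤ x | 53, p) = 0.05. For x = 10 (18.9%, the largest non-significant count) it is 29.9%.

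**Acute toxicity, if the 9.3 rule and the test count the same events.**
- 12% of 53 is 6.36, so a completed trial has at most 6/53 (11.3%). P(X ≥ 6 | 53, 0.12) = 0.62, so the p-value is at least 0.62.
- At 7 to 10 events (13.2% to 18.9%) the rule says terminate while the test is non-significant.
- Bias with one check at 53 patients and a true 12%: E(X | X ≤ 6) / 53 = 8.7%; P(X ≤ 6) = 0.545.
- Bias with a check after every patient from the 17th (an assumed start; 2/16 = 12.5% crosses 12%, 2/17 = 11.8% does not), again at a true 12%: 28% of trials complete, with a mean observed rate of 7.4%.
- At a true 20%, P(X ≤ 6 | 53) = 7.3% of trials complete with one check, and 2.5% with checks from patient 17.

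**What 53 patients can exclude.** At 6/53 the exact one-sided 95% upper limit is 21.1%, and the two-sided 95% interval is 4.3% to 23.0%.

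**The case against.** Section 9.4.2 never says that a non-significant result will be taken as proof of no added toxicity, and it does not itself name 12%. It already plans a 95% interval, which carries most of the information needed. The stopping rule gives real protection: it would end a trial truly at 12% in 45% to 72% of cases under the two checking schemes above, so not every feature of the plan leans towards a finding of safety.

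Most of this is fair, but it does not remove the problem. The hypothesis is worded as no significant increase and no rate to be excluded is given, so non-rejection is the only result of the test that matches the claim. The interval is planned only for acute toxicity, and no limit is tied to a conclusion.

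Four stronger readings are tempting, and the documents do not support them.
- A reader might infer that a non-significant acute result is guaranteed. That needs the rule and the test to count the same events. Section 3.4 limits the rule to clinically significant, treatment-related events; 9.3 says grade 3; 9.4.2 says grade 3 or greater over 24 months; 2.4.1 defines acute as up to 90 days. With these differences a trial could satisfy the rule and still reach 11 events.
- A reader might apply the 50% figure to acute toxicity. Under the rule, on the same events, only 7.3% or 2.5% of trials at a true 20% would complete. The figure describes events the rule does not count, such as late toxicity.
- A reader might infer that no one-sample test could support a safety claim. A reversed null, set at a prespecified unacceptable rate, would support a bounded one.
- A reader might infer that patients lost early are counted as event-free. The documents do not say how losses are handled.

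**Conclusion.** The concern holds in this form: the toxicity test in 9.4.2 lacks a margin or unacceptable rate, and as worded it invites reading non-rejection as absence of added toxicity.

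For events outside the stopping rule, the chance of a non-significant result with 53 patients is 65% at a true 18% and 50% at a true 20%. Across n = 47 to 53 and one-sided 0.05 or 0.025, the chance at a true 20% is 50% to 67%. These figures assume the 12% reference rate and a one-sided level borrowed from the PSA-CR test.

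For acute toxicity the conclusion is conditional on the rule and the test counting the same events. In that case the test cannot show an excess, and at a true 12% the mean observed rate in completed trials is 8.7% or 7.4%, depending on how often the rule is applied. Whether the condition is met cannot be settled from the current text, because the four sections define the events differently.

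**What to change.** In 9.4.2, do not draw the safety conclusion from non-rejection. Replace the one-sample test with the exact one-sided 95% upper confidence limit, reported separately for acute and for late grade 3 or greater toxicity, and claim only that rates above the limit are excluded. Give an example in the plan so that the reach of the trial is clear in advance: 6/53 excludes rates above 21.1% (two-sided 95% interval 4.3% to 23.0%).

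State beside the acute estimate that it is conditional on the trial not having stopped under 9.3 and is therefore biased low.

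Reconcile grade, attribution and time window across 2.4.1, 3.4, 9.3 and 9.4.2, so that it is clear which events the rule, the estimate and the late-toxicity analysis each count.

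The cost is a change of wording, with no extra patients or data. The stated safety claim becomes weaker: with 53 patients the trial can bound the toxicity rate but cannot show that it has not risen above 12%.
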